### 9.7.2 Statistical methods

#### 9.7.2.1 Analysis of primary endpoints

The primary endpoints are the number of Adverse Drug Reactions (ADRs), incident neoplasms, and incident T2D from baseline (week 0) up to end of study (week 520).

Frequencies of ADRs during the study period will be summarised by MedDRA SOC and PT. This summary is displayed with number and proportion of patients with at least one event, number of event and event rate (events per 100 patient-years of exposure).

The primary objective of the study is to evaluate safety of once weekly dosing of Sogroya® (somapacitan) in AGHD patients over a study period up to 10 years, and analysis of ADRs will be one of the tools for achieving this. Adverse drug reactions will be analysed using descriptive statistics based on the ‘on treatment’ observation period (primary evaluation) and ‘in-study’ observation period (secondary evaluation) within the study period. The ADRs will be summarised by treatment, MedDRA (Medical Dictionary for Regulatory Activities) system organ class and MedDRA preferred term. The descriptive statistics will include the number and percentage of patients who experienced ADRs, the number of events and rate per 100 person years. ADRs will be listed by treatment and patient with information on severity, relationship to study product and demographics. ADRs with onset before first dosing will be reported in a separate listing.

In addition, incidence rates will be calculated for the endpoints Neoplasm and Diabetes Mellitus type 2.

Results will be reported separately for treatment-naïve and prevalent users of GH replacement therapy, and patients with a history of neoplasia and diabetes mellitus 2 will be addressed in stratified analyses.

For historical reference the primary evaluation, i.e. the on-treatment analysis, will be compared to the same results reported from the Nordinet® IOS database. It is not expected that there will be big differences in the baseline characteristics between the Nordinet® adult population and the population investigated in this study. If there are big differences between baseline characteristics, a matching procedure will be considered when making the comparison. In addition, a sensitivity analysis will be performed, restricting the primary evaluation to a European population only.

Protocol  
 Study ID: NN8640-4515  
 UTN: U1111-1264-8642  
 EU PAS No: Pending

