## 7 Rationale and background

Sogroya® (somapacitan) is a recombinant human GH analog developed by Novo Nordisk, indicated for replacement of endogenous GH in AGHD. Replacement therapy with recombinant GH is the standard of care for patients with AGHD. Sogroya® (somapacitan) is a long-acting GH product developed for once weekly subcutaneous (s.c.) administration.

Replacement therapy with once-weekly somapacitan and once-daily somatropin differ from endogenous GH release under normal physiological conditions.

In clinical phase 3 trials, IGF-I levels obtained with somapacitan were within the age-adjusted normal reference range with temporary peaks above the upper limit of normal range for a small subset of patients. Importantly, modestly and transiently elevated IGF-I levels in GH replacement therapy have not been linked to adverse effects in published literature nor in the somapacitan phase 3 trials.

Even after over 20 years of adult GH replacement, evidence suggesting that rhGH replacement in adults increases cancer risk or accelerates recurrences of tumours in the hypothalamic-pituitary region remains unclear; With conflicting results in the literature, the overall effect of rhGH replacement on the development of diabetes is also unclear. Somapacitan has been studied in AGHD patients for up to 86 weeks. Thus, the safety information during longer period of treatment is limited.

If patients taking GH replacement report significant QoL benefits and/or there are objective improvements, such as in cardio-vascular risk markers, BMD, body composition, or physical activity tolerance, then GH treatment can be continued indefinitely. Therefore, further investigations, including long-term surveillance studies after regulatory approval are essential to improve our understanding of the safety and effectiveness of prolonged exposure to Sogroya®.

As part of the marketing authorisation of Sogroya®, Novo Nordisk has received a requirement from the Committee for Medicinal Products for Human Use (CHMP) under European Medicines Agency (EMA) to conduct a non-interventional PASS to investigate long-term safety of Sogroya® in patients with AGHD.

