**Figure 1 Study Design**

**Note:** symbol (  ) Represents interim reporting

The study is planned to collect a broad variety of safety and other clinical parameters data generated during routine clinical care visits and other relevant clinical contacts (e.g. phone calls between patient and clinical site) in AGHD patients treated with commercially available Sogroya® (somapacitan). The duration of the study is planned with patient participation for 5 years or longer up to a total study duration of 10 years, if possible. The main purpose of the study is to observe patients for long-term safety. It is however well known that adult patients on GH therapy, often interrupt or discontinue treatment. Due to this expected dropout from treatment, and in the context of the duration of the study, patients switching from or discontinuing treatment with Sogroya® (somapacitan) will be offered continuation in the study in order to collect post treatment data.

The current study will compare data from a non-interventional registry study (NordiNet® IOS) which was monitoring the long-term use of once daily Norditropin® as a historical comparison group consisting of approximately 2300 AGHD patients enrolled in Europe between 2006 and 2016.

The sample size estimation for this study is based on the incidences for neoplasms reported in Nordinet® IOS. It is estimated that a sample size of 400 patients will be required to rule out the doubling of incidence for neoplasms in patients treated with Sogroya® (somapacitan).

Data on concomitant medication, medical history (adult/ childhood onset of GHD), laboratory parameters including but not limited to hepatic, renal, heart and diabetes status as well as data on neoplasms and medication errors will be collected as part of this study if available per routine clinical practice in order to evaluate safety. Other data which are already available in the medical records or being obtained as part of routine clinical practice, such as IGF- I /IGFBP-3 values, measures of body composition and bone health and PROs, will be collected to support the evaluation of clinical parameters.

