## 9.2 Setting

### 9.2.1 Study population

Patients for this study will be included globally from centres in countries where patients will be treated with Sogroya® within the planned recruitment timelines of the study.

Planned number of patients to be included globally: 400

Planned number of patients to complete the study: 400

Anticipated number of patients to be included in each country: depending on availability and commercial uptake of Sogroya® in relevant countries.

Planned time period for the study: 15 Dec 2022-15 Dec 2032

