#### **Continuous secondary endpoints:**

For the following secondary endpoints, the change will be estimated by length of follow-up and by treatment duration. Patients on oral oestrogen therapy and patients with childhood-onset GHD will be addressed in stratified analyses. The effect of a previous GH replacement therapy on the health-related quality of life will be checked in stratified analyses.

- Change in IGF-I SDS
- Change in weight
- Change in BMI
- Change in waist circumference
- Change in waist-hip ratio
- Change in lipid profile
- Change in HbA1C
- Change in bone density
- Change in bone mineral content
- Change in total body fat mass
- Change in truncal fat mass
- Change in lean body mass
- Change in body fat percentage
- Change in VAT
- Change in liver function
- Change in PRO score (TRIM-AGHD)

Protocol  
 Study ID: NN8640-4515  
 UTN: U1111-1264-8642  
 EU PAS No: Pending

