#### **9.7.2.3 Analysis of exploratory endpoint(s)**

The number of sick days and physician visits in the AGHD WSI will be converted into visits per year. The impact on productivity and ability to do regular activities will be analysed in the same way as the secondary endpoint Change in PRO score (TRIM-AGHD).

The number of anti-diabetic medications will be presented in descriptive tables for the subgroup of patients with diabetes mellitus type 2 at baseline by length of follow-up and by treatment duration.

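### The neoplasm and type 2 diabetes rates should also be reported by time since first Sogroya dose, as a cheap addition that matches the duration split already planned for lesser endpoints

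*Protocol*

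**What the plan says.** The reason for the study is in section 7: "Somapacitan has been studied in AGHD patients for up to 86 weeks. Thus, the safety information during longer period of treatment is limited". The primary objective (section 8.1) is long-term safety with a focus on neoplasms and type 2 diabetes.

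For these two endpoints section 9.7.2.1 says: "In addition, incidence rates will be calculated for the endpoints Neoplasm and Diabetes Mellitus type 2". The same section adds several splits. One reads "Results will be reported separately for treatment-naïve and prevalent users of GH replacement therapy"; the others are stratified analyses for a history of neoplasia or type 2 diabetes, on-treatment and in-study periods (defined in section 9.7.1), and a sensitivity analysis restricted to Europe. None is by exposure duration.

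A duration split is stated elsewhere. For continuous secondary endpoints such as weight and waist circumference, section 9.7.2.2 says that "the change will be estimated by length of follow-up and by treatment duration". Section 9.7.2.3 presents anti-diabetic medication counts "by length of follow-up and by treatment duration". Annex 2 item 5.3, on categorising exposure by time windows, is marked not applicable. The interim reports (section 9.7.3) follow the approach of the final report.

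**The concern.** An incidence rate pools all person-time, so a patient-year soon after starting counts the same as one in year nine. Individual follow-up can run from one week to ten years (section 9.1.1.1). Entry is spread over five years, and the protocol expects losses from treatment: "It is however well known that adult patients on GH therapy, often interrupt or discontinue treatment". Late exposure is therefore the smaller part of the denominator in the on-treatment analysis, which is the primary evaluation and the one compared with NordiNet IOS.

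If a neoplasm or diabetes risk emerges only after several years, the overall rate moves much less than the late rate. A reader could then take a modest overall ratio as reassurance about prolonged use. Weight and waist circumference would have been examined by duration, while the two primary events would not.

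**Working it through.** **Nearest figure in the plan.** Section 9.5 gives 0.9 to 3.9% as the 95% interval for an observed 2% in 400 patients, as the basis for ruling out a doubling. The exact binomial interval for 8/400 is 0.87 to 3.90%, so it is reproduced. It is a proportion without a time unit and says nothing about when events occur.

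**Inputs from the protocol.** 400 patients (section 9.2.1: "Planned number of patients to be included globally: 400"); ten years in all (section 9.2.1: "Planned time period for the study: 15 Dec 2022-15 Dec 2032"); recruitment ends 15 Dec 2027, five years after first patient first visit (section 6); on-treatment time ends at discontinuation (section 9.7.1).

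**Assumptions.** Uniform accrual, first dose at enrolment, and constant discontinuation of 0, 10 or 20% per year.

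**Formula.** Patient-years = 400 × ∫ exp(−λt) A(t) dt, with λ = −ln(1 − annual proportion), A(t) = 1 up to year 5 and (10 − t)/5 from year 5 to year 10.

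If the rate doubles after a threshold, the overall ratio = (PY before + 2 × PY after) / total PY = 1 + share after the threshold.

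**Threshold at year 5**

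| Discontinuation per year | Total PY | PY to year 5 | PY after year 5 | Share to year 5 | Overall ratio |
|---|---|---|---|---|---|
| 0% | 3000 | 2000 | 1000 | 67% | 1 + 1000/3000 = 1.33 |
| 10% | 2054 | 1555 | 499 | 76% | 1 + 499/2054 = 1.24 |
| 20% | 1439 | 1205 | 233 | 84% | 1 + 233/1439 = 1.16 |

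With linearly front-loaded or back-loaded accrual as well, the share to year 5 ranges from 60 to 88% and the ratio from 1.12 to 1.40.

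**Threshold at 86 weeks** (86 × 7/365.25 = 1.648 years)

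| Discontinuation per year | Share within 86 weeks | Share beyond | Overall ratio |
|---|---|---|---|
| 0% | 22.0% | 78.0% | 1.78 |
| 10% | 29.5% | 70.5% | 1.71 |
| 20% | 38.3% | 61.7% | 1.62 |

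**Interim cuts** (uniform accrual, no loss). At 3 years there are about 360 PY, none beyond year 5. At 6 years there are about 1400 PY, of which about 40 lie beyond year 5.

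**What a split would show.** Assume 1.0 event per 100 PY up to year 5 and 2.0 after, with expected events rounded for the exact Poisson limits.
- No discontinuation: overall 1.33 (0.95 to 1.82); early 1.0 (0.61 to 1.54); late 2.0 (1.22 to 3.09).
- 10% per year: overall 1.24 (0.83 to 1.85); early 1.0 (0.59 to 1.67); late 2.0 (0.96 to 3.68), the last on about 500 PY.

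The rise is visible in the point estimates, but the late interval is wide.

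**The case against.** **The analysis plan may supply it.** Banding a descriptive rate by time is ordinary detail for a statistical analysis plan, which is not shown here, and nothing in section 9.7.2.1 forbids it. This stands in part: it rules out calling the protocol wrong. But the section does list its splits, and the protocol states a duration split for other endpoints. Annex 2 item 5.3 points the same way. That item carries limited weight, because item 10.4 of the same checklist answers no to stratified analyses that section 9.7.2.1 plainly includes.

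**The stronger reading fails.** A reader might infer that each event gets a single pooled rate, that a late risk would vanish in it, and that the rate mainly reflects the 86 weeks already studied. The documents do not support this. Several strata and two observation periods are planned, and the effect is dilution. In the scenarios above, 62 to 78% of on-treatment time lies beyond 86 weeks, the only evidence gap the protocol names. Year 5 is an illustrative threshold that the protocol does not set.

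**The other endpoints differ in kind.** Repeated measurements need a time axis to be reported at all, whereas a rate does not. So the contrast with sections 9.7.2.2 and 9.7.2.3 is an unevenness and no contradiction.

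**A late band has its own weaknesses.** The early and late intervals overlap even with no discontinuation, and patients still on treatment after year 5 are a selected group. Both points stand and limit the band to description.

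**First dose is not always at enrolment.** Section 9.2.4 admits patients already on Sogroya. By time since first dose, their observed time sits later than computed here, so the true late share could be larger and the dilution smaller.

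**Conclusion.** The point holds as a cheap improvement. As described, the neoplasm and type 2 diabetes rates have no split by exposure duration, in a study whose purpose is long-term safety and whose lesser endpoints have one. Under uniform accrual, first dose at enrolment and 0 to 20% discontinuation per year, 67 to 84% of on-treatment time falls in the first five years. A doubling confined to later exposure would appear as an overall ratio of about 1.16 to 1.33; one starting at 86 weeks, as about 1.62 to 1.78. The discontinuation range and accrual pattern are assumptions, and patients already on Sogroya would shift the figures towards less dilution. No number in the protocol is disputed.

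**What to change.** In section 9.7.2.1, alongside the overall rate, report events, patient-years and rates with 95% confidence intervals for neoplasm and type 2 diabetes by time since first Sogroya dose, for example up to 86 weeks, 86 weeks to 5 years, and beyond 5 years.

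- Count only observed time. Patients already on Sogroya enter their band at enrolment (delayed entry), because adverse events are collected only from consent (section 9.2.7.1).
- Show the table for both the on-treatment and in-study periods.
- Include it in the final report and, where the bands hold person-time, in the interim reports. On the figures above, the 3-year cut cannot fill the last band and the 6-year cut barely does.
- Align Annex 2 item 5.3.
- Describe the latest band as descriptive, and say that long-term stayers are a selected group.

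The cost is one table from exposure and event data the study already collects, plus the wording. The protocol does not list the date of first Sogroya dose as a separate item for patients already on the product, so confirm that the eCRF holds it; the observation periods in section 9.7.1 need it in any case. The downside is wide intervals in the latest band.

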### **The study population is characterized through the exclusion criteria:**

Criterion no. 1 is to ensure that a patient only counts once in the data analyses.

Criterion no. 2 serves to protect patient safety and rights.

Criterion no. 3 is to exclude patients with hypersensitive to Sogroya® (somapacitan) or any of its excipients in accordance with the summary of product characteristics (SmPC)

Criterion no.4 is to exclude patients with any evidence of active malignancy. Any pre-existing malignancy should be inactive, and its treatment complete prior to instituting therapy with Sogroya® (somapacitan) in accordance with the SmPC.

Criterion no.5 is to exclude patients with increased risk of mortality, in accordance with the SmPC.

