## 9.7 Data analysis

### 9.7.1 Definition of analysis sets

The safety analysis will be based on the Safety Analysis Set (SAS). The SAS will consist of all patients exposed to Sogroya® (somapacitan) during study period. Two observation periods are defined:

- on-treatment: from first administration until last study contact, discontinuation of Sogroya®, or withdrawal of informed consent, whichever comes first
- in-study: from first administration until last study contact, or withdrawal of informed consent, whichever comes first

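### For incident neoplasm, the zero-lag on-treatment window that serves as primary evaluation and as the NordiNet comparison can bias the rate low; it needs an explicit, lagged window with the in-study rate beside it

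*Protocol*

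**What the plan says.** Protocol section 9.7.1 defines two observation periods. The first is "on-treatment: from first administration until last study contact, discontinuation of Sogroya", or withdrawal of consent, whichever is earliest. No lag after the last dose is given. The second is "in-study: from first administration until last study contact, or withdrawal of informed consent, whichever comes first", which runs on past discontinuation.

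Section 9.7.2.1 covers three primary endpoints (ADRs, incident neoplasm and incident type 2 diabetes) and gives their time frame as "from baseline (week 0) up to end of study (week 520"). For ADRs it makes on-treatment the primary evaluation and in-study the other: "observation period (secondary evaluation) within the study period". For the other two it says only: "In addition, incidence rates will be calculated for the endpoints Neoplasm and Diabetes Mellitus type 2", with no period named. It then states: "For historical reference the primary evaluation, i.e. the on-treatment analysis, will be compared to the same results" from NordiNet IOS.

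Section 9.1 expects treatment to be stopped or interrupted often. It provides that "patients switching from or discontinuing treatment with" Sogroya will be offered further participation so that data after treatment can be gathered. Section 9.5 bases the sample size on neoplasm incidence in NordiNet.

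**The concern.** A window that closes on the day of discontinuation suits reactions that appear soon after a dose. Neoplasm is different in two ways. A tumour that began on treatment may be diagnosed later. A suspected tumour may also be the reason for stopping, in which case censoring depends on the outcome being counted. In both cases the person-time up to stopping is kept and the event is not.

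Neoplasm is singled out in the primary objective, and the NordiNet comparison is the only external reference. The analysis assigned to that comparison is the one that leaves out the post-treatment data the study sets out to collect.

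**Working it through.** **Inputs.** The windows are in section 9.7.1. The role of each window and the incidence-rate measure are in section 9.7.2.1. The endpoint time frame is in sections 9.1.1.1 and 9.7.2.1. The 2% reference and 400 patients are in section 9.5. The protocol gives no discontinuation rate, no share of neoplasms diagnosed after stopping, and no NordiNet counting window.

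**1. The plan's own figure.** Table 1 gives 0.9% to 3.9% for an observed 2% in 400 patients, that is 8/400. The exact (Clopper-Pearson) limits are:
- lower: Beta quantile 0.025 with parameters 8 and 393 = 0.87%
- upper: Beta quantile 0.975 with parameters 9 and 392 = 3.90%

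The figure reproduces, and 3.90% lies below 2 × 2% = 4%. It is a proportion of patients and names no observation window. The planned measure is a rate per person-time, so this figure cannot size the window problem.

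**2. Which window governs neoplasm.**
- The endpoint runs to end of study.
- The incidence-rate sentence names no window.
- The comparison sentence stands under a heading that covers all three primary endpoints and equates the primary evaluation with on-treatment.
- Nothing places neoplasms after discontinuation in the primary evaluation or in the NordiNet comparison.

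The natural reading is that on-treatment governs neoplasm, but this has to be inferred.

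**3. Effect on the rate.** Let O be the neoplasms dated inside the window, P the on-treatment person-years, and d the neoplasms that arose or were under work-up before stopping but are dated after it. The planned rate is O/P. Crediting the displaced events to the exposure that preceded them gives (O + d)/P. P is the same in both, so

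planned / credited = O/(O + d) = 1 − s, with s = d/(O + d).

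| Assumed s | Factor on the rate |
|---|---|
| 0% | 1.00 |
| 10% | 0.90 |
| 25% | 0.75 |
| 50% | 0.50 |

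**4. Effect on the comparison.** With displaced shares s for this study and n for NordiNet,

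observed rate ratio = true ratio × (1 − s)/(1 − n).

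For a true ratio of 2:
- n = 0 (NordiNet counts the later events): 2 × 0.90 = 1.80, 2 × 0.75 = 1.50 and 2 × 0.50 = 1.00 for s = 10%, 25% and 50%.
- n = s (same cut-off, same displacement): 2.00, no bias in the ratio.
- n = 25%, s = 10%: 2 × 0.90/0.75 = 2.40, bias upward.

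The direction of any bias in the comparison therefore depends on a window that the protocol does not give.

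**5. What a lag does.** It adds to the numerator the displaced events recovered within the lag, plus any background events there. It adds the lag person-years to the denominator. The documents give no input for a number.

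**The case against.** **The primary/secondary split is written only for ADRs.** This stands. That it governs neoplasm rests on the heading and the comparison sentence. If the sponsor meant otherwise, the text still has to say so.

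**The tumours are not lost to the study.** This stands. They leave the primary evaluation and the comparison, but the in-study period can count them while the patient remains under observation.

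**Stopping on suspicion is not in the documents.** This stands. Section 9.2.4 ("Any pre-existing malignancy should be inactive, and its treatment complete prior to instituting therapy with" Sogroya) explains an entry criterion and is no rule for stopping. Nor does the protocol say whether onset or diagnosis dates a neoplasm. Section 11.2 has signs recorded before a diagnosis is available, so a tumour worked up on treatment might carry an on-treatment onset. The latency route to displacement needs no stopping rule.

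**A lag length and a dating rule can be left to the SAP.** That is true of those details. The window and its role in the comparison are fixed in the protocol itself.

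**Making in-study the sole primary window has its own cost.** This stands. Time off drug, or on another GH product, pulls a true excess towards background.

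Two stronger readings are tempting, and the documents support neither.

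- A reader might infer that losing a case or two reverses the exclusion of doubling, because 8/400 has an upper limit of 3.90% and 9/400 one of 4.23%. That removes cases from a fixed denominator of 400, whereas the planned measure is a rate whose person-time also stops at discontinuation. Doubling appears only as sample-size rationale, and the ENCePP checklist (item 2.1.4) marks hypotheses to be tested as not applicable.
- A reader might infer that a large share of follow-up after stopping itself shows a low bias. Take 400 × 7.5 = 3000 patient-years (7.5 years being the midpoint of 5 to 10) and assume that 10% or 15% discontinue per year. About 0.70 or 0.59 of the time is then on treatment: 2100 or 1770 patient-years. With 11 neoplasms in-study, 8 of them on treatment, the in-study rate is 11/3000 = 3.67 per 1000 patient-years. The on-treatment rate is 8/2100 = 3.81 or 8/1770 = 4.52, which is higher. On-treatment falls below in-study only if the share of events lost exceeds the share of time lost.

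**Conclusion.** The concern holds in limited form. The protocol fixes a zero-lag on-treatment window as the primary evaluation and as the only one compared with NordiNet, and read with its heading this covers incident neoplasm, whose endpoint runs to end of study. The on-treatment rate can be biased low by the factor 1 − s. This rests on the assumption that some neoplasms arise or come under work-up on treatment and are dated after stopping. The real value of s cannot be derived from the documents, and neither can the size or direction of any effect on the NordiNet comparison. The documents do not show that a conclusion about doubling would change. A change of wording is warranted because neoplasm is a named focus of the primary objective and the data needed are already to be collected.

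**What to change.** For incident neoplasm only:

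- State in section 9.7.2.1 which observation window applies, and whether onset or diagnosis date places an event in it.
- Extend the on-treatment period by a fixed lag after the last dose, its length set in advance, counting both events and person-time in the lag.
- Report the already-defined in-study rate beside it in the NordiNet comparison, with post-treatment time split by later GH use.
- State NordiNet's counting window and match it as far as its data allow. Where it cannot be matched, say so with the result.
- Keep the unlagged on-treatment rate as a sensitivity analysis.

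Leave ADRs on the current definition.

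The cost is protocol and SAP wording plus a few more rate tables, since follow-up after discontinuation is already planned. The downside is that some time and events off drug or on another GH product enter the lagged and in-study rates and can dilute a true effect. Hence the split by later GH use and the retained unlagged rate.
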